Kuvan®(sapropterin dihydrochloride) is a synthetic form of the cofactor BH4 (tetrahydrobiopterin) for the enzyme phenylalanine hydroxylase (PAH). PAH hydroxylates phenylalanine to form tyrosine. BH4 activates residual PAH enzyme, improving normal phenylalanine metabolism and decreasing phenylalanine levels in responders. Kuvan®(sapropterin dihydrochloride) was approved by the US Food and Drug Administration (FDA) in 2007 for use in treatment of the genetic disorder phenylketonuria at doses of 5-20mg/kg once daily. To our knowledge, the role of Kuvan®(sapropterin dihydrochloride) in treating diastolic dysfunction in human subjects has not been studied.

Hypothesis:

Treating patients with underlying diastolic dysfunction with Kuvan®(sapropterin dihydrochloride), in addition to standard care for heart failure will improve metabolic parameters and echocardiographic parameters of diastolic function compared to standard care for heart failure alone

Specific Aims:**Primary Aim:**

Study the effect of Kuvan®(sapropterin dihydrochloride) supplementation in addition to standard care for heart failure compared to standard care alone on maximum VO₂ consumption in patients with diastolic dysfunction from baseline to three months on medication. This parameter will be obtained via cardiopulmonary exercise stress testing.

Secondary Aim:

Study the effect of Kuvan®(sapropterin dihydrochloride) supplementation in addition to standard care for heart failure compared to standard care alone on additional metabolic parameters obtained from CPET (Ve/VCO₂), echocardiographic parameters of diastolic dysfunction (see below), and quality of life (measured by Kansas City Cardiomyopathy Questionnaire) for the duration of the study.

Relevance to VA:

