The functional and economic burden of congestive heart failure on the Veterans' health system is unparalleled. It is the number one reason for admission in this system, with over 100,000 hospitalizations for this diagnosis and a re-admission rate of near 20% in the last fiscal year. Additionally, it accounted for over 1,000,000 outpatient encounters over the same time period⁹. The cost of this disease is greater than \$37 billion to the United States healthcare system¹⁰. Accordingly, The CHF Quality Enhancement Research Initiative [QUERI] was created to improve both survival and quality of life in veterans with heart failure. The efforts of this initiative have been focused on systolic dysfunction, due to the paucity of positive studies on diastolic dysfunction. If successful, our study will improve the quality of life and outcomes for the large number of veterans affected by this disease.

Study Design

This proposal describes a randomized crossover pilot study in 30 subjects at the Providence VA Medical Center to address the hypothesis that Kuvan®(sapropterin dihydrochloride) supplementation is an effective treatment strategy in patients with heart failure with preserved ejection fraction. The subjects will be randomized into two groups; Kuvan®(sapropterin dihydrochloride), in addition to best current clinical practices versus best current clinical practices alone. The randomization process will occur in a one to one fashion. At the end of three months, there will be a wash out period of one week (during which both groups will not take the study medication) prior to the groups being crossed over. Data will again be collected and reviewed at monthly intervals and at the end of the study.

Inclusion Criteria

1. Male and female U.S. Veteran patients over the age of eighteen, with echocardiographic findings of \geq Grade 2 diastolic dysfunction [as per American Society of Echocardiography guidelines] and
2. Diagnosis of hypertension, diabetes (type 1 or type 2), or heart failure in medical records.

3. Eligible subjects must be ambulatory (not dependent on any ambulatory assist devices including cane or walker).

Exclusion Criteria

1. Any history of documented ejection fraction <50%
2. Significant COPD (defined as oxygen-dependent COPD)
3. Acute coronary syndrome within the past three months defined by EKG changes and biomarkers of myocardial necrosis (ie. elevated troponin) in the setting of chest pain or an anginal equivalent)

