12 week visit (three hours)- Brief history and physical exam, Kansas City Cardiomyopathy Questionnaire, labwork for biomarkers (as documented above), chemistry, lipid, and liver panels, BNP, echocardiogram, and CPET testing.

13 week visit (thirty minutes)- Patients will be crossed over to the second arm of the study. They will receive a brief history and the second group will be provided with a supply of Kuvan®(sapropterin dihydrochloride) tablets or powder.

19 week visit (thirty minutes)- Brief history and physical exam.

25 week visit (three hours)- Brief history, Kansas City Cardiomyopathy Questionnaire, labwork for biomarkers, chemistry, lipid, and liver panels, BNP, echocardiogram, and CPET testing.

Telephone calls will be made at week 1, 3, 9, 16, and 22 to assess for patient compliance, provide any necessary support, and screen for side effects.

	Screening Visit	Baseline Visit	Week 1	Week 3	Week 6	Week 9	Week 12	Week 13	Week 16	Week 19	Week 22	Week 25
Contact	Clinic	Clinic	Tel	Tel	Clinic	Tel	Clinic	Clinic	Tel	Clinic	Tel	Clinic
Limited History/Physical	x				x		x	x		x		x
Assess Medication Compliance					x		x			x		x
Labwork	x						x					x
Echo	x						x					x
CPET		x					x					x
KCCQ	x						x					x
Exacerbation History		x	x	x	X	x	x	x	x	x	x	x
Adverse Event Monitoring			x	x	X	x	x	x	x	x	x	x

Table 1. Follow-up Clinic Visits, telephone calls, and schedule of studies. CPET, cardiopulmonary exercise stress test; KCCQ, Kansas City Cardiomyopathy questionnaire; Tel, telephone contact; Labwork: basic chemistry panel, complete blood count, lipid panel, liver function tests, and the following biomarkers: BNP, glutathionylated myosin binding protein C, adiponectin, aldosterone, endothelin-1, NT-procollagen III, uric acid, DROM

Subject Reimbursement:

Subjects will be reimbursed for every visit they attend. Attendance to visits 1 and 2 (screening and baseline visits), as well as visits 4 and 7 (all three hour visits) will be reimbursed fifty dollars. Attendance to visits 3, 5, and 6 will be reimbursed twenty-five dollars.

Specific Study Procedures:

Questionnaire: The Kansas City Cardiomyopathy questionnaire will be used and is attached (Appendix B).

Echocardiogram: Transthoracic echocardiography uses ultrasound technology to evaluate heart structure and function. Measurements to be collected include:

1. Tissue Doppler Index (Septal and Lateral E')
2. E Velocity
3. E/E' ratio
4. E/A Ratio
5. Pulmonary Vein Tracing (S/D Ratio, A-AR duration, AR Velocity)

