Any adverse events that are immediately life-threatening, cause permanent or lasting harm, or require a hospitalization will receive a “serious” classification as per defined by the BioMarin Standard Language for Adverse Event Report (above, and Appendix D). All serious AEs and unanticipated problems will be reported to the IRB as soon as possible, but no later than 5 days from notification. If an event is possibly, probably or definitely related to the intervention, it will be classified as intervention-related. Any incidental finding discovered during follow up visits or imaging will be graded based on level of severity. Severe findings (as determined by evaluating physician) will be referred to the Emergency Department for further evaluation. Findings determined to be low or moderate severity will be relayed to both the subject and his or her primary care physician or cardiologist.

Sample size determination**Primary Aim:**

This study is a pilot study, and as a result a sample size determination is not necessary.

Data Collected see: Protocol Addendum: Information Privacy and Security Items and Safety**Data Analysis Plan see: Protocol Addendum: Information Privacy and Security Items and Safety**

Aim 1: The primary outcome will be the difference in maximum VO₂ consumption obtained from a cardiopulmonary exercise test at baseline, 3 months and conclusion of the study [Δ VO₂ consumption] between Kuvan®(sapropterin dihydrochloride) use versus not. Descriptive statistics (mean, standard deviation, median, inter-quartile range, and frequency distribution) will be calculated to summarize, at baseline, participants' demographic and medical history, and the primary outcome of interest (peak Vo₂) according to randomized intervention sequences. We will ensure a balanced randomization is accomplished using t or nonparametric (Wilcoxon's) tests whenever

each test's distribution assumption is appropriate. We will use the variants of statistical methods (t tests and linear models) specifically designed to analyze crossover clinical trials to assess changes in peak VO₂ in response to Kuvan®(sapropterin dihydrochloride) supplementation in addition to current best practices versus current best practices alone.

Secondary Aims: The CPET measures and molecular biomarkers will be analyzed using the same crossover analysis models for crossover clinical trials¹⁶.

Data storage and sharing see: Protocol Addendum: Information Privacy and Security Items and Safety

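### With no exercise test after the washout, does the primary analysis overstate the drug effect on peak VO₂ by half?

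*Combined protocol and SAP*

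**What the plan says.** The Study Design section opens: "This proposal describes a randomized crossover pilot study in 30 subjects". On allocation it says: "The randomization process will occur in a one to one fashion". That makes 15 patients per sequence. Group 1 takes the drug first and Group 2 takes it second. After three months "there will be a wash out period of one week", off drug for both groups.

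Table 1 and the visit list place the cardiopulmonary exercise test at the baseline visit, week 12 and week 25. The week 13 entry reads "13 week visit (thirty minutes)- Patients will be crossed over to the second arm of the study" and adds a brief history and drug supply, with no exercise test.

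The Primary Aim concerns the effect "on maximum VO₂ consumption in patients with diastolic dysfunction from baseline to three months on medication". Aim 1 of the Data Analysis Plan states: "The primary outcome will be the difference in maximum VO₂ consumption obtained from a cardiopulmonary exercise test at baseline, 3 months and conclusion". The outcome is written as a delta and compared between drug use and no use. On method it says: "We will use the variants of statistical methods (t tests and linear models) specifically designed to analyze crossover clinical trials". It does not say which test is the reference for a second-period change. The heading of that section also points to an addendum that is not among the documents.

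**The concern.** The outcome is worded as a change, and a change needs a starting value. Period 1 has a clean one, because the week 0 test is off drug for everyone. Period 2 has none of its own. An analyst who took the most recent test as the starting value would use week 12.

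That does no harm in Group 2, whose week 12 test is off drug. In Group 1 the week 12 value already contains the drug effect, so the fall after stopping would be counted as a negative control-period change. The effect would then enter Group 1's contrast twice.

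At stake would be the size of the primary estimate and some power. The section on the importance of the knowledge gained says that an ineffective result will argue against the drug, so lost power would matter as well as an inflated effect.

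**Working it through.** The plan gives no effect size, SD, power or derivation of N = 30, so there is no figure of its own to reproduce. The check is which estimate each reading of the text produces.

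**Inputs.** From the documents: tests at weeks 0, 12 and 25 (W0, W12, W25); 15 patients per sequence; Group 1 on drug at week 12, Group 2 on drug at week 25. Assumed: drug effect τ, period shifts p1 and p2 relative to week 0, independent within-patient errors with SD s, and no carryover unless stated.

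**Expected values, as departures from week 0**

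| | W0 | W12 | W25 |
|---|---|---|---|
| Group 1 | 0 | τ + p1 | p2 |
| Group 2 | 0 | p1 | τ + p2 |

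The crossover estimate is ½ × [mean(D1 − D2) in Group 1 − mean(D1 − D2) in Group 2], where D1 and D2 are the responses in periods 1 and 2.

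**Reading A: successive changes.** D1 = W12 − W0 and D2 = W25 − W12.
- Group 1: D1 − D2 = (τ + p1) − (p2 − τ − p1) = 2τ + 2p1 − p2.
- Group 2: D1 − D2 = p1 − (τ + p2 − p1) = −τ + 2p1 − p2.
- Estimate: ½ × [2τ − (−τ)] = 1.5τ, whatever the period shifts.
- D1 − D2 = 2·W12 − W0 − W25, with variance (4 + 1 + 1)s² = 6s². SE = √(¼ × 2 × 6s²/15) = 0.447s.

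**Reading B: change from week 0 in both periods.** D1 = W12 − W0 and D2 = W25 − W0.
- D1 − D2 = W12 − W25, so week 0 cancels.
- Estimate: ½ × [(τ + p1 − p2) − (−τ + p1 − p2)] = τ.
- Variance 2s². SE = √(¼ × 2 × 2s²/15) = 0.258s.

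**Reading C: period-end values compared directly.** D1 = W12 and D2 = W25. This is the same contrast as B, with the same estimate and SE.

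**Reading D: linear model on all three tests**, with subject, visit and an on-drug indicator.
- The indicator is (0, 1, 0) in Group 1 and (0, 0, 1) in Group 2. Its subject mean is ⅓ for everyone, and its visit means are 0, ½ and ½.
- With subject and visit removed it becomes (0, ½, −½) in Group 1 and (0, −½, ½) in Group 2. Week 0 gets zero weight.
- The coefficient is ½ × [mean(W12 − W25) in Group 1 − the same in Group 2], which is exactly B and C.

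**Reading E: baseline to week 12 only, as a parallel comparison.** Estimate τ, SE = √(2 × 2s²/15) = 0.516s. It ignores week 25.

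**A against B, C and D.** The estimate is 1.5 times as large and the SE is √3 = 1.73 times as large, so the test statistic falls to 1.5/1.73 = 0.87 of its value. With an assumed τ = 0.75s and two-sided 5% tests, power is 68% for A, 80% for B to D and 29% for E. A simulation of 40,000 trials (assumed τ = 1, s = 1.2) agrees:
- A: mean 1.50, SE 0.536, power 0.77, type I error 0.049.
- B to D: mean 1.00, SE 0.309, power 0.88, type I error 0.050.

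**Carryover.** If a fraction c of the effect persists in Group 1 to week 25, A gives (1.5 − c/2)τ and B to D give (1 − c/2)τ.

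**Would a week 13 test have helped?** With it, the contrast (W12 − W0) − (W25 − W13) has variance 4s² and SE √(¼ × 2 × 4s²/15) = 0.365s. Under the same error assumptions that is noisier than the 0.258s already available. It is also a clean baseline only if the drug effect has gone within a week.

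**Which reading does the text support?** For exercise testing, the Baseline visit section and Table 1 use the word baseline only for the test before randomization. Aim 1 lists baseline, three months and conclusion as separate tests. Group 2 starts the drug at week 13, so its change from that baseline to three months on medication runs from week 0 to week 25, which is reading B. The commitment to crossover t tests and linear models leads to C or D. No sentence leads to A.

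**The case for a change.** The best case for a change is that a primary outcome should not leave its reference test to inference. Successive change is a possible reading: for Group 2, the last test before three months on drug is week 12, and nothing explicitly forbids treating Group 1 the same way. Crossover methods still need a defined response for each period, so naming the methods does not by itself supply one. The trial is described without placebo or blinding, so a definition chosen after seeing the data could be chosen for its result. The same models are planned for the secondary exercise measures and biomarkers, and laboratory tests, echocardiography and the questionnaire also have no measurement after the washout. One sentence would settle the matter.

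Part of this stands. The reference test is not named, and the factor of 1.5 is exact for successive changes without carryover. But the factor belongs to one reading and is not a consequence of the design. Reading A departs from the plan's own use of the word baseline, and reading E discards the crossover that the plan says it will analyse. The remaining routes are algebraically one estimator, so choosing among them after the data are seen cannot move the result when all three tests are complete.

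**Conclusion.** The concern does not call for a change. The plan's wording is compatible with an inflation of anything from 0% to 50%, but the 50% needs a step that the plan does not prescribe. Change from week 0, period-end comparison and the all-tests linear model all estimate τ, with SE 0.258s. The sentence that would close the gap describes an analysis that the plan already allows.

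This rests on no carryover, complete data, 15 patients per sequence and independent within-patient errors. The power figures also rest on the assumed τ = 0.75s. Under successive changes the bias would be proportional to τ: it vanishes when the drug does nothing, and type I error stays near 5%. Carryover would lower every one of the crossover estimates by the same c/2 of τ, so it is a separate question from the choice of reference test.

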Members of the investigator team will explain the study to the potential participants and answer any questions that they may have regarding the study protocol. The investigator will make it clear that the protocol is research as well as voluntary and that declining participation will in no way affect further evaluation or access to clinical care. Participants will also be informed that they may withdraw their consent at any point throughout the study. Patients will be given adequate time to read the consent form and discuss its contents with research personnel before signing the consent form. They will also be provided with a phone number through which adverse events should be reported. Participants will then be asked to sign an IRB-approved written consent document and health insurance portability and accountability act (HIPAA) agreement, which will allow data pertinent to the study to be collected.

Following the completion of informed consent, the baseline visit will be scheduled within one week of study enrollment.

2. Baseline visit:

At this visit, the subjects will undergo a brief interview to assess for recent changes in health status. Cardiopulmonary exercise testing will be performed to establish the subjects' baseline. The patients will then be randomized (in a 1:1 fashion as mentioned above) to either Group 1, who will begin the study by taking the study medication in addition to their current medication regimen, or Group 2, who will begin the study by continuing their current medication regimen without the study medication. The subjects in Group 1 will be provided with their preference of either a supply of 100mg Kuvan®(sapropterin dihydrochloride) tablets or Kuvan®(sapropterin dihydrochloride) in the powder form. This visit will last three hours.

The subjects in Group 1 will be instructed to initiate the study medication at the weight-based dose of 10mg/kg (rounded to the nearest hundred) with meals (at the same time each day) for one week beginning the following day (day 1). After telephone contact (table 2) with a study team member on day 7, assuming no adverse effects are noted, the patient will be instructed to increase their daily dose to 20mg/kg (rounded to the nearest hundred) with meals (at the same time each day) for the remainder of the study period. The subjects in Group 2 will not be started on the study medication until after the 'wash-out period' as described in the study design

Study Drug:

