Blood Samples Transfer see: Protocol Addendum: Information Privacy and Security Items and Safety

Patient safety:

Human Subjects Research

This Human Subjects Research meets the definition of “Clinical Research”. This study is a clinical trial, and will be registered on Clinicaltrials.gov.

Protection of human subjects

Potential risks

Questionnaires and record keeping. There is no specific physical risk to completing the quality of life questionnaires. All records will be kept confidential, kept in locked cabinets, and identified by study code only in the working databases.

Phlebotomy. Phlebotomy for blood drawing is associated with temporary pain at this site and may result in bruising at the needle insertion site. Risks of the procedure include: vasovagal reaction during needle puncture; bruising at the phlebotomy site; and the possibility of skin or soft tissue infection at the needle puncture site.

Echocardiogram. Standard approaches to performing transthoracic echocardiography will be utilized, which may induce transient discomfort as the ultrasound probe is pressed against the upper chest.

Cardiopulmonary exercise testing. The testing may cause shortness of breath, fatigue, muscle discomfort, and very rarely (<1:1,000) may be associated with heart attack or death.

Therapeutic risks

Treatment with Kuvan®(sapropterin dihydrochloride).

Kuvan®(sapropterin dihydrochloride) is currently FDA approved for the treatment of phenylketonuria (PKU). The most common side effects include: headache, peripheral edema, arthralgia, polyuria, agitation, dizziness, nausea, pharyngitis, abdominal pain, upper abdominal pain, and upper respiratory tract infection.

In clinical trials the most common adverse reactions ($\geq 4\%$ of patients) were: headache, rhinorrhea, pharyngolaryngeal pain, diarrhea, vomiting, cough, and nasal congestion.

In the postmarketing period, the most common adverse reactions due to Kuvan are oropharyngeal pain, pharyngitis, esophageal pain, gastritis, dyspepsia, abdominal pain, nausea and vomiting. Hypersensitivity reactions including anaphylaxis and rash have been reported. Most hypersensitivity reactions occurred within several days of initiating treatment. Two cases of hyperactivity have been reported, including one case in a patient who received an accidental overdose of Kuvan.

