Patients will be contacted via phone at weeks 1, 3, 9, 16, and 22. During these phone calls, patients will be asked the questions outlined in Table 2. Additionally, the patients will be seen in person in a research clinic during weeks 6, 12, 13, 19, and 25. At these clinic visits, patients will be asked the questions listed in Table 3. The research team will meet every 4 weeks to review study progress and adverse events. Additionally, all data will be reviewed to assure that no physiological findings warrant immediate intervention. If so, the participant will be contacted and advised of the findings and offered assistance with appropriate referrals. Data from the echocardiogram, laboratory tests and cardiopulmonary exercise testing procedures will be reviewed by the investigators and any unusual or adverse findings will be communicated to the participant's primary care physician. Adverse events will be defined as per the BioMarin Standard Language for Adverse Event Report (below, and attached in Appendix D) and reported to the IRB in accordance with the rules regulating each severity class (expected vs. unexpected, serious vs. other, related vs. unrelated).

BioMarin Standard Language for Adverse Event Reporting: IST Program, Kuvan

According to the ICH definition, an adverse event (AE) is any untoward medical occurrence in a patient or clinical investigation subject administered a pharmaceutical product, and that does not necessarily have a causal relationship with this treatment. An AE can therefore be any unfavorable and unintended sign (including an abnormal laboratory finding), symptom, or disease temporally associated with the use of a medicinal (investigational) product, whether or not considered related to the investigational product.

This definition includes intercurrent illnesses or injuries that represent an exacerbation (increase in frequency, severity, or specificity) of pre-existing conditions. Whenever possible, it is preferable to record a diagnosis as the AE term rather than a series of terms relating to a diagnosis.

Adverse event information will be collected in an ongoing fashion through patient reporting AEs to their physician or health care provider. Seriousness and relatedness will be assessed by the treating physician, with appropriate reporting.

A designated primary contact person based at the treatment center will be responsible for the collection and reporting of AEs for patients participating in the program.

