Table 2 - Telephone Monitoring:

Side Effects – fevers, nausea, vomiting, diarrhea, rhinorrhea?
Compliance and barriers to compliance?
Have there been changes in previous medication regimen?
Weight loss/gain?
Is dyspnea improved, worse, or unchanged?
Is there any subjective change in exercise tolerance?
Have there been any doctor's visits or hospitalizations?

Table 3 - Brief History and Physical:

Vital Signs:
Temperature
HR
Respiratory Rate
Oxygen Saturation
Weight
Limited Exam:
HEENT: JVD
CVS: S3
Chest: Crackles
Abd: HJR, Pulsatile Liver
Ext: Edema?
Side Effects – fever, nausea, vomiting, diarrhea, rhinorrhea?
Compliance and barriers to compliance?
Have there been changes in previous medication regimen?
Weight loss/gain?
Is dyspnea improved, worse, or unchanged?
Is there any subjective change in exercise tolerance?
Have there been any doctor's visits or hospitalizations?

References

- 4) Hernandez AF, et al. Clinical effectiveness of beta-blockers in heart failure: findings from the OPTIMIZE-HF (Organized Program to Initiate Life-saving Treatment in Hospitalized Patients with Heart Failure) Registry. *J Am Coll Cardiol*. 2009; 53:184-192
- 6) Pitt B, et al. Spironolactone for Heart Failure with Preserved Ejection Fraction. *N Engl J Med* 2014; 370:1383-1392
- 8) Silberman GA, et al. Uncoupled Cardiac Nitric Oxide Synthase Mediates Diastolic Dysfunction. *Circulation* 2010; 121: 519-528.

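### The scripted questions asked before the Group 1 dose increase at day 7 do not prompt for rash or other skin and swelling signs of allergy, or for dizziness or fainting

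*Combined protocol and SAP*

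**What the plan says.** Under Data and safety monitoring the protocol states: "During these phone calls, patients will be asked the questions outlined in Table 2". The same section assigns the Table 3 questions to the clinic visits. Each table has one side-effect item. Table 2 reads "Side Effects – fevers, nausea, vomiting, diarrhea, rhinorrhea" and Table 3 reads "Side Effects – fever, nausea, vomiting, diarrhea, rhinorrhea". Neither has an item for other symptoms.

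The Baseline visit section ties the Group 1 step from 10 mg/kg to 20 mg/kg to one of these calls: "After telephone contact (table 2) with a study team member on day 7, assuming no adverse effects are noted".

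On known reactions, Therapeutic risks says: "The most common side effects include: headache, peripheral edema, arthralgia, polyuria, agitation, dizziness", among others. It adds: "Hypersensitivity reactions including anaphylaxis and rash have been reported", and that most such reactions came within several days of starting treatment.

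The Screening visit section ends participation if, in the hour after the test dose, the subject shows signs of allergy or defined hypotension. Dizziness and syncope are the symptoms attached to the blood-pressure fall in that definition.

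**The concern.** The prompts overlap poorly with the reactions that the protocol itself treats as most consequential. Fever is asked about although Therapeutic risks does not name it. Rash, itching, hives, swelling, dizziness and fainting are not asked about. Rash and dizziness are named as reactions, and all six belong to the test-dose exit criteria (swelling as angioedema, fainting as syncope).

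The gap matters most at day 7. That contact is by telephone, so staff cannot see a rash, and it is the scheduled check before the daily dose goes up. A subject with a mild rash or lightheadedness who does not connect it with the drug could answer every listed question truthfully without mentioning it. What is at stake is subject safety at one decision point, and even recording of symptoms at later contacts.

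**Working it through.** No sample-size or power figure is involved. The check sets the sections side by side.

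**1. Are the tables operative?** Yes. Data and safety monitoring says that subjects are asked the Table 2 questions on calls and the Table 3 questions at visits, and the Baseline visit section cites Table 2 for the day-7 call.

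**2. Match of the five prompts (fever, nausea, vomiting, diarrhea, rhinorrhea) to the protocol's own lists.**

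| Source | Terms | Named in the side-effect item |
|---|---|---|
| Therapeutic risks, most common side effects: "headache, peripheral edema, arthralgia, polyuria, agitation, dizziness, nausea, pharyngitis, abdominal pain, upper abdominal pain, and upper respiratory tract infection" | 11 | 1 (nausea) |
| Therapeutic risks, at least 4% of trial patients: "headache, rhinorrhea, pharyngolaryngeal pain, diarrhea, vomiting, cough, and nasal congestion" | 7 | 3 (rhinorrhea, diarrhea, vomiting); 3/7 = 43% |
| Therapeutic risks, postmarketing list | 8 | 2 (nausea, vomiting) |
| Screening visit, signs of allergic reaction | 8 | 2 (nausea, emesis) |
| Screening visit, symptoms attached to the blood-pressure fall | 2 (dizziness, syncope) | 0 |

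Of the eight allergic signs, the six not named are pruritus, rash, hives, angioedema, abdominal cramping and a heart rate above 100. Heart rate is measured at visits under Table 3 but cannot be on a call. Table 3 as printed lists neither blood pressure nor a skin examination, so the visit content does not close the gap.

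**3. Timing.** Group 1 starts the drug on day 1 and is called on day 7. Most hypersensitivity reactions are said to occur within several days of starting, which falls in that interval. The test-dose observation lasts one hour and cannot cover it.

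**4. Could another Table 2 item pick these reactions up?** The remaining items cover compliance, medication changes, weight, dyspnea, exercise tolerance, and doctor's visits or hospitalizations. The last would reveal a reaction that led to care. None asks about a rash, itching or a dizzy spell that did not.

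**5. How many contacts?** There are 5 calls (weeks 1, 3, 9, 16, 22) and 5 clinic visits (weeks 6, 12, 13, 19, 25), so 5 + 5 = 10 scripted contacts per subject. With 30 subjects randomised 1:1, Group 1 has 30/2 = 15, hence about 15 day-7 calls before a dose increase.

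**The case against.** The strongest reply is that the protocol does not rely on this line alone. Monitoring for Adverse Events tells subjects to report any change in medical condition at each follow-up contact, which includes day 7 and comes close to an open question. Subjects also receive a telephone number for adverse events. Follow up visits has them evaluated for adverse reactions at every visit, and Table 1 marks adverse-event monitoring at every contact after baseline. Emergency visits and admissions are tracked through the medical record. The adverse-event definition covers any untoward occurrence, and the five terms may be meant as examples.

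Much of this stands. Omitted reactions can be reported, and a severe one would probably surface through care received. What remains is that the general instruction depends on the subject speaking up, while five other symptoms are asked about by name. Nothing in either table marks the terms as examples, and the general instruction is not part of the call questions.

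Two stronger readings are tempting. A reader might infer that five negative answers release the dose increase. The Baseline visit section instead makes it depend on the whole contact and on no adverse effects being noted. A reader might also infer that no allergic sign from the test-dose criteria is asked about, but nausea and emesis are on that list and are prompted.

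**Conclusion.** The point holds as a gap in active questioning, not as a bar to reporting. Both tables leave out rash, itching, hives and swelling, and dizziness and fainting. At the day-7 Table 2 call, detecting these relies on the subject volunteering them, unless they led to medical care. The direct exposure is about 15 calls, assuming full enrolment and equal allocation. The documents describe this day-7 step for Group 1, and the point is limited to that. It also assumes that staff ask the tables as written, as Data and safety monitoring says.

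Two further inferences should not be drawn. One is a small overall percentage of named reactions covered: the Therapeutic risks lists contain near-duplicates, such as several terms for throat pain and two for abdominal pain, so the denominator is arbitrary. Against the list of reactions in at least 4% of patients the item covers 3 of 7. The other is that the trial's adverse-event profile would reflect the script instead of the drug. Volunteered reports and record tracking still feed it, and no stated aim or analysis concerns adverse-event rates.

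The change is worth making for subject safety. It does not bear on the peak VO₂ analysis.

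**What to change.** In the side-effect item of both tables:

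- Add an open question, such as *any new symptom or change since the last contact?*
- Add explicit prompts for rash, itching, hives or swelling, and for dizziness or fainting.
- Keep the existing prompts. Headache and the other reactions named under Therapeutic risks are optional additions.
- Use the same wording in drug and no-drug periods, so that symptoms are sought equally in both.

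The sponsor should also reconcile the Screening visit, Baseline visit, Therapeutic risks and Monitoring for Adverse Events sections with Tables 2 and 3, and state which answers count as adverse effects at the day-7 call. That is the sponsor's clinical decision; no dose or stopping rule is proposed here.

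The cost is rewording two tables and the call form, a minute or two per contact, and more minor events recorded.
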